### **3.1.1. Dose Finding Phase**

#### **3.1.1.1. Starting Doses for Axitinib and MK-3475 (Dose Level 1)**

The starting doses (Dose Level 1) are axitinib 5 mg BID and MK-3475 2 mg/Kg IV Q3W in three-week cycles.

#### **3.1.1.2. Criteria for Dose Finding**

Dose finding will follow an “Up-and-Down” design, using doses of MK-3475 and axitinib as shown in Table 1.

**Table 1. Dose Levels in the Dose Finding Phase**

Dose Level	MK-3475	Axitinib
1 (Starting Dose Level)	2 mg /kg IV q3wk	5 mg BID
-1	2 mg /kg IV q3wk	3 mg BID

BID: twice daily; q3wk: every 3 weeks

Possible dose finding scenarios based on the starting (1) dose level tolerability are illustrated in [Table 2](#). DL-1 will be explored only if the MTD is exceeded already at DL1.

In this dosing algorithm there are up to 2 potential dose levels (DL): (DL-1) MK-3475 2 mg/kg q3wk + axitinib 3 mg BID and (DL1) MK-3475 2 mg/kg q3wk + axitinib 5 mg BID.

Alternative doses, schedule(s) and PK time points may be reconsidered during the study based on the emerging safety and PK data.

There are several potential dosing finding sequences for MK-3475 + axitinib. The specific sequence to be followed depends upon the number of patients enrolled in the study and the number of DLTs observed at each specific dose combination. The sequences are mutually exclusive, meaning only one of the sequences will be followed through the course of the study. Some possible sequences are listed below in [Table 2](#).

**Table 2. Possible Dose Finding Sequences**

Possible sequences starting at Dose Level 1									
DL1									
DL1 → DL-1									
DL1 → DL-1 → DL1									

Dosing will begin at DL1 and possibly de-escalated to DL -1 according to Table 3. Dose escalation from DL -1 back to DL 1 will be allowed as long as DL 1 has not been determined to have exceeded the MTD. The escalation/de-escalation rules will follow the mTPI method (see [Section 9.2](#)). Briefly, the mTPI method relies upon a statistical probability algorithm, calculated using all patients treated in prior and current cohorts at the same dose level to determine where future cohorts should involve dose escalation, no change in dose, or dose de-escalation. The detailed dose-finding rules based on the mTPI are illustrated in Table 3.

**Table 3. Detailed Dose Escalation/De-Escalation Scheme**

		Number of patients treated at current dose									
		1	2	3	4	5	6	7	8	9	10
Number of toxicities	0	NA	NA	E	E	E	E	E	E	E	E
	1	NA	NA	S	S	S	E	E	E	E	E
	2	NA	D	S	S	S	S	S	S	S	S
	3		DU	DU	D	D	S	S	S	S	S
	4			DU							
	5				DU						
	6					DU	DU	DU	DU	DU	DU
	7						DU	DU	DU	DU	DU
	8							DU	DU	DU	DU
	9								DU	DU	
	10									DU	

E = Escalate to the next higher dose

S = Stay at the current dose

D = De-escalate to the next lower dose

U = The current dose is unacceptably toxic

NA = Not Applicable. The first three patients will have to be evaluable for DLT before assigning DL for the next patient

MTD = 30%

As an example, if the total number of patients treated at DL1 is 3 the following dosing rules are applied:

- 0 - 1 DLT → remain at the same dose (DL1);
- 2 DLTs → de-escalate to DL-1 and allow for possible escalation back to DL1;

- 3 DLTs → de-escalate to DL-1 and consider DL1 as intolerable.

If the dose is de-escalated to DL-1 and the total number of patients then treated at DL-1 is 3 the following dosing rules are applied:

- 0 DLTs → escalate back to DL1;
- 1 DLT → remain at the same dose (DL-1);
- 2-3 DLTs → de-escalation not possible consider DL-1 as intolerable.

Rules for dose-finding, using the mTPI method, include the following:

- The target enrollment cohort size is 3 patients. The first 3 patients treated at each dose level will initiate dosing sequentially, at least 2 days apart from each other to allow for the initial evaluation of toxicities and tolerability. If the first 2 patients experience a DLT prior to enrollment of the third one, the dose level will be deemed intolerable and the dose level will be de-escalated. If there are no safety concerns, any additional patients enrolled to this dose cohort will not be required to initiate dosing sequentially.
- The next cohort can be enrolled when all patients at the current dose cohort have been evaluated for 6 weeks (ie, the first 2 treatment cycles), or experience a DLT, whichever comes first.
- If a patient withdraws from study treatment before receiving at least 75% of the planned first two cycles dose of axitinib or two infusions of MK-3475 within the DLT observation period for reasons other than study drug-related toxicity, another patient will be enrolled to replace that patient at the current dose level.
- The dose-finding component of the trial is completed when 10 DLT-evaluable patients have been treated at the highest dose associated with DLT rate <0.33. It is estimated that approximately 20 DLT-evaluable patients will need to be enrolled to reach 10 DLT-evaluable patients at the estimated MTD.
- The proposed doses, schedule, and PK timepoints may be reconsidered and amended during the study based on the emerging safety and pharmacokinetic data.
- The RP2D will be confirmed in the Dose Expansion Phase, taking into account the MTD determination from the Dose Finding Phase, and other factors related to safety, efficacy, and PK/PD involving all available data from test cohorts.

No intrapatient dose escalation will be permitted in the Dose Finding Phase.

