### **Statistical Methods:**

#### Up-and-Down Design with the mTPI Method

The escalation/de-escalation rules will follow the modified toxicity probability interval (mTPI) method. Briefly, the mTPI method relies upon a statistical probability algorithm, calculated using all patients treated in prior and current cohorts at the same dose level) to determine when future cohorts should involve dose escalation, no change in dose, or dose de-escalation.

Rules for dose finding, using the mTPI method, include the following:

- The target enrollment cohort size is 3 patients. The first 3 patients at each dose level will initiate dosing sequentially, at least 2 days apart, to allow for the initial evaluation of toxicities and tolerability. If the first 2 patients experience a DLT prior to enrollment of the third, the dose level will be deemed intolerable the dose level will be de-escalated. If there are no safety concerns, any additional patients enrolled to this dose cohort will not be required to initiate dosing sequentially.
- The next cohort (target 3 patients) can be enrolled when all patients at the current dose cohort have been evaluated for 6 weeks (ie, the first two treatment cycles), or experience a DLT, whichever comes first.

- If a patient withdraws from study treatment before receiving at least 75% of the planned first two cycles (6 weeks) doses of axitinib or two infusions of MK-3475 within the DLT observation period for reasons other than study drug-related toxicity, another patient will be enrolled to replace that patient at the current dose level.
- The dose-finding component of the trial is completed when at least 10 DLT-evaluable patients have been treated at the highest dose associated with a DLT rate <0.33. It is estimated that approximately 20 DLT-evaluable patients will need to be enrolled to reach 10 DLT-evaluable patients at the estimated MTD.
- The proposed doses, schedule and PK time points may be reconsidered and modified during the study based on the emerging safety and PK data.

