19. **Adverse Events:** Adverse events should be documented and recorded at each visit using NCI CTCAE version 4.03. For SAEs, the active reporting period to Pfizer or its designated representative begins from the time that the patient provides informed consent, which is obtained prior to the patient's participation in the study, ie, prior to undergoing any study-related procedure and/or receiving investigational product, through and including 90 calendar days after the last administration of the investigational product and before initiation of a new anti-cancer treatment. The prolonged follow up is due to the pharmacokinetic properties of the investigational product MK-3475. SAEs experienced by a patient after the active reporting period (see [Section 8.1.1](#)) has ended should be reported to the Sponsor if the Investigator becomes aware of them; at a minimum, all SAEs that the Investigator believes have at least a reasonable possibility of being related to study drug are to be reported to the Sponsor. AEs (serious and non serious) should be recorded on the Case Report Form (CRF) from the time the patient has taken at least one dose of study treatment through last patient visit (Day 28 after last dose). If a patient begins a new anticancer therapy, the AE reporting period for non serious AEs ends at the time the new treatment is started. Pregnancy or breast feeding that occur during the trial, within 120 days of discontinuing treatment with MK-3475, or within 28 days after the cessation of study treatment if the patient begins a new anticancer therapy, whichever is earlier, should be reported as in [Section 8.4 \(Exposure During Pregnancy\)](#).

20. **Concomitant Medications/Treatments:** Concomitant medications and treatments will be recorded from 28 days prior to the start of study treatment and up to 28 days after the last dose of study treatment. All concomitant medications should be recorded in the CRF including supportive care drugs (eg, anti-emetic treatment and prophylaxis), and the drugs used to treat adverse events or chronic diseases, and non-drug supportive interventions (eg, transfusions).

21. **Registration:** Patient number and dose level allocation operated by Pfizer Inc. Required information: site and patient identifiers and demographic information. Study treatment (either single agent axitinib for patients in Lead-in or axitinib in combination with MK-3475 for all other patients) should begin within 7 days of registration.

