Pharmacokinetic assessment: MK-3475 and axitinib do not have competing elimination/metabolism pathways, hence an overt PK interaction between the two drugs is not anticipated. However, pharmacokinetic assessments will be conducted in this study to confirm the absence of drug-drug interactions. To understand the PK effects of MK-3475 on axitinib, a 7-day lead-in period of single-agent axitinib will be included prior to Cycle 1 in all patients in the Dose Finding Phase and in at least 8 patients in the Dose Expansion Phase of the study. Axitinib has a plasma half life of 2.5-4.1 hours and is expected to reach steady-state within 2 to 3 days of dosing. MK-3475 has a long plasma half-life (21-28 days) and trough concentrations increase with successive doses until steady state, which is expected within 5 months of MK-3475 dosing. The administration of single agent MK-3475 to this patient population is not considered in this trial. Therefore, the effect of axitinib on MK-3475 will be evaluated by comparing MK-3475 pharmacokinetics at steady-state in the presence of axitinib with those reported for MK-3475 alone in prior studies. At least 8 patients (target is 8 PK evaluable patients) from the Dose Expansion Phase will participate in PK assessments, therefore these patients will undergo the 7-day lead-in period for axitinib. There will be no lead-in period for the remaining patients in the Dose Expansion Phase.

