### **9.1. Analysis Sets**

The following patient sets will be assessed.

- Safety analysis set.

The safety analysis set includes all enrolled patients who receive at least one dose of axitinib or MK-3475.

- Per protocol analysis set (evaluable for DLT).

All enrolled patients who are eligible, receive at least one dose of axitinib and MK-3475, and who either experience DLT during the first two cycles, or complete the observation period for the first two cycles of treatment (6 weeks). Patients who withdraw from study treatment before receiving at least 75% of the planned first two cycles doses of axitinib or two infusions of MK-3475 within the DLT observation period due to reasons other than treatment related adverse events are not evaluable for DLT. A patient who is unable to start at the assigned Cycle 1 Day 1 dose level after the lead-in period will not be evaluable for DLTs but will be evaluated for safety and efficacy.

- Response evaluable analysis set.

All patients who receive study treatment with an adequate baseline tumor assessment will be considered evaluable for anti-tumor efficacy using standard RECIST 1.1 criteria.

- PK analysis set.

The PK concentration population is defined as all treated patients who have at least 1 concentration of either of the study drugs.

The PK parameter analysis population is defined as all treated patients who have at least 1 of the PK parameters of interest of any of the study drugs.

- Biomarker analysis set.

The biomarker analysis set is defined as all treated patients who have at least one screening biomarker assessment, and have received at least one dose of any study drug. Analysis sets will be defined separately for blood-based and tumor tissue-based biomarkers.

If mutational profiling is performed on samples derived from the biomarker analysis set, the analysis may be limited to screening samples only.

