6.2. Safety Endpoints

6.2.1. Dose Limiting Toxicity (DLT) (Primary Endpoint for Dose Finding Cohorts)

Severity of AEs will be graded according to NCI CTCAE v 4.03. AEs meeting one of the definition criteria in protocol Section 3.1.2 occurring in the DLT observation period (6 weeks post C1D1) which are attributable to one or both study drugs will be classified as DLTs.

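### The two-DLT stop is tied to enrolment of the third patient, so at the permitted 2-day spacing the 7-day axitinib lead-in leaves it no countable DLT to act on

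*Protocol*

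**What the plan says.** The Protocol Summary (Statistical Methods) sets the stagger: "The first 3 patients at each dose level will initiate dosing sequentially, at least 2 days apart". Section 3.1.1.2 repeats it, gives early evaluation of toxicity and tolerability as its purpose, and attaches the stop: "If the first 2 patients experience a DLT prior to enrollment of the third one, the dose level will be deemed intolerable", after which the dose is lowered.

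Four other provisions fix the timing:

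- **Lead-in.** Section 3.1: "a 7-day lead-in period of single-agent axitinib will be included prior to Cycle 1 in all patients in the Dose Finding Phase".
- **DLT window.** The primary endpoint in Protocol Section 2.2 is DLTs in the first two cycles. SAP Section 6.2.1 counts qualifying events "occurring in the DLT observation period (6 weeks post C1D1").
- **Start of study treatment.** Footnote 21 of the Schedule of Activities defines it as "either single agent axitinib for patients in Lead-in or axitinib in combination with MK-3475 for all other patients", and says it "should begin within 7 days of registration". Section 5.1 forbids giving study drug before the sponsor has confirmed enrolment in writing.
- **Visit window.** Section 5.2.4.1 lets the Day 1 dose move by up to 3 days either way for administrative reasons.

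On evaluability, Protocol Section 9.1 says that a patient "unable to start at the assigned Cycle 1 Day 1 dose level after the lead-in period will not be evaluable for DLTs", though the patient still counts for safety and efficacy.

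**The concern.** The stop is there to spare a third patient the combination when the first two have both had a DLT. Enrolment has to come before the lead-in, and no DLT can be counted until the lead-in is over. If patients start at the shortest permitted interval, the moment at which the stop is checked falls before either earlier patient can have a countable event. Followed to the letter, the rule protects nobody.

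The text also does not say whether the stagger refers to the first lead-in dose or to C1D1. If it means the lead-in, the visit window can bring two patients' first MK-3475 infusions onto the same day or reverse their order. An acute infusion reaction, which Section 5.5.2 places during or shortly after infusion, might then not be seen before the next patient is infused.

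At stake is the exposure of about one patient per newly opened level, with at most two levels (Table 1). The MTD analysis is not affected.

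**Working it through.** **Plan's own figure.** No operating characteristic is given for this stop. The nearest figure is the Table 3 entry for 2 DLTs in 2 patients, which is D (de-escalate). Under an assumed Beta(1,1) prior the posterior is Beta(3,1), with distribution function q³. Using the cut points 0.25 and 0.33 from Section 9.2.1, the unit probability masses are:

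- under-dosing: 0.25³ / 0.25 = 0.0625
- proper dosing: (0.33³ − 0.25³) / 0.08 = 0.254
- over-dosing: (1 − 0.33³) / 0.67 = 1.439

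The largest is over-dosing, so D is reproduced. The decision is sound; the question is when it can be triggered.

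**Timeline at minimum spacing.** Inputs: spacing 2 days, lead-in 7 days, registration 0 to 7 days before first dose. Day 0 is patient 1's first axitinib dose.

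| Patient | Lead-in start | Nominal C1D1 |
|---|---|---|
| 1 | 0 | 7 |
| 2 | 2 | 9 |
| 3 | 4 | 11 |

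- Patient 3's enrolment: 4 − (0 to 7) = day −3 to day 4.
- Patient 3's lead-in start relative to the first nominal MK-3475 dose in anyone: 4 − 7 = −3 days.
- Countable days for patients 1 and 2 at that enrolment: 0 and 0. The chance of the stop firing is zero.
- Using the visit window to bring C1D1 forward does not help: patient 2's earliest date is 9 − 3 = day 6, after day 4, and the stop needs DLTs in both patients.
- If the stagger means C1D1 dates 2 days apart, the same table results, because each patient still enrols before a 7-day lead-in.

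**Spacing needed.** For patient 2 to have one combination day before patient 3 enrols, their starts must differ by 7 + 1 + (0 to 7) = 8 to 15 days.

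**Gap between first infusions if the stagger means the lead-in.** Keep the full lead-in and let each C1D1 slip by d = 0, 1, 2 or 3 days. C1D1 then falls on days 7–10, 9–12 and 11–14, and the adjacent gap is 2 + d₂ − d₁. It is below 2 days whenever d₂ < d₁, in 6 of 16 pairs: three leave 1 day, two fall on the same day, one is reversed. This counts permitted dates and is not a probability.

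**After moving the anchor to patient 3's first MK-3475 dose (day 11).** Patients 1 and 2 have 11 − 7 = 4 and 11 − 9 = 2 countable days. Assume independent patients and a constant hazard h = −ln(1 − p)/42, where p is the 6-week DLT rate. The documents give no onset distribution.

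P(stop) = [1 − exp(−4h)] × [1 − exp(−2h)]

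| p | P(stop), 2-day spacing | P(stop), 7-day spacing (14 and 7 days) | Both have a DLT within 6 weeks (p²) |
|---|---|---|---|
| 0.30 | 0.0334 × 0.0168 = 0.06% | 0.65% | 9% |
| 0.50 | 0.0639 × 0.0325 = 0.21% | 2.3% | 25% |

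**Sensitivity to early onset.** Suppose a share s of DLTs falls evenly in the first 7 days. Given that both patients have a DLT at some point, the stop fires with probability (4s/7) × (2s/7) = 8s²/49. This is 0.45% for s = 1/6 (uniform over 42 days), 4.1% for s = 0.5 and 16.3% for s = 1. Multiplying by p² = 0.09 gives 0.04%, 0.4% and 1.5% at p = 0.30.

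**The case against.** The strongest reply is that the sentence is a conditional instruction and promises no observation period. Two days is a floor, and the rule works at longer gaps. Other controls act at the same point: Section 5.1 requires written sponsor permission before each patient is dosed and has the sponsor announce the next possible enrolment date; Section 9.7 has DLT findings discussed as they arise; and the next cohort waits until current patients have completed 6 weeks or had a DLT. Re-anchoring leaves a stop that almost never fires. The infusion-gap problem disappears if the stagger already means C1D1, and the 2-day gap occurs anyway on the nominal schedule. The lead-in is also not the only cause: if enrolment means registration 7 days before dosing, the stop would fail at 2-day spacing without any lead-in. Finally, this stage of the trial is over.

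Most of this stands as a limit on size. The lead-in is sufficient to disable the stop, but the word enrolment contributes. Later toxicity will still be caught by the 6-week gate and ongoing review. What does not stand is that the other controls fill the gap. Permission to dose is mandatory, but its timing is left to the sponsor, and neither Section 5.1 nor Section 9.7 sets a minimum interval.

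One side effect is also fair. A third patient moved to dose level −1 (DL-1) after a 5 mg lead-in would have axitinib PK profiles at two doses. SAP Section 8.3.4.1 allows for this through dose-normalisation and exclusion from the median plots.

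**Conclusion.** The concern holds, at minor severity and with high confidence. At the spacing the protocol permits, the two-DLT stop cannot operate under either reading of the stagger. This follows from the documents' own dates and needs no modelling assumption.

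The benefit of repair is modest. The 0.06% and 0.21% figures rest on independence and a constant hazard; earlier onset raises them, to 1.5% at a DLT rate of 0.30 if every DLT fell in the first week. The firmer gains are that patient 3's 7-day lead-in becomes observation time on the earlier patients at any spacing, and that a 2-day separation of first infusions becomes a requirement.

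**What to change.** In the Protocol Summary and Section 3.1.1.2:

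- Require the first MK-3475 doses (C1D1) of the first three patients at each level to be at least 2 days apart, and say that the visit window may not shorten this.
- Apply the stop if both earlier patients have a DLT before the third patient's first MK-3475 dose, and state that the third patient is then not given the combination at that level.
- State what that patient receives: DL-1 if available, otherwise axitinib alone or withdrawal. State also whether the patient is replaced.
- State that this patient is not DLT-evaluable (Section 9.1) and, if no MK-3475 is given, counts for safety only. SAP Section 5.3 requires a dose of both drugs for response evaluability and SAP Section 6.1 times PFS from the first MK-3475 dose, which conflicts with the mention of efficacy in Protocol Section 9.1.

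Because primary data collection is complete, the step for this trial is to list actual first MK-3475 dates for the first three patients at each level opened. SAP Section 8.3.2 already lists first-dose dates but does not name the drug. The rule itself should be corrected before it is reused.

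The cost is two rule sentences, a short statement on patient 3 and one listing. If C1D1 slips for administrative reasons, patients 2 and 3 wait at most 3 days on lead-in axitinib: the latest dates, days 10, 12 and 14, keep the 2-day gaps and stay inside each window. A longer delay for toxicity in patient 1 could extend that wait. The Lead-in Day 7 PK profile is unaffected.

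A 7-day spacing is not proposed. It would put nominal C1D1 on days 7, 14 and 21, moving patient 3 by 21 − 11 = 10 days, for a stop probability of only 0.65% to 2.3%.

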### **3.1.2. DLT Definition**

Severity of adverse events will be graded according to NCI CTCAE version 4.03 (see [Appendix 3](#)). For the purpose of Dose Finding, any of the following adverse events occurring during the DLT observation period (6 weeks) that are attributable to one or both study drugs will be classified as DLTs:

- Hematologic:

Grade 4 neutropenia;

Febrile neutropenia, defined as absolute neutrophil count (ANC)  $<1000/\text{mm}^3$  with a single temperature of  $>38.3$  degrees C (101 degrees F) or a sustained temperature of  $\geq 38$  degrees C (100.4 degrees F) for more than one hour;

Grade  $\geq 3$  neutropenic infection;

Grade  $\geq 3$  thrombocytopenia with bleeding;

Grade 4 thrombocytopenia.

- Non-hematologic:

Grade  $\geq 3$  non-laboratory toxicities despite maximum supportive therapy.

Grade  $\geq 3$  hypertension despite maximal medical therapy.

- Non-hematologic Grade  $\geq 3$  laboratory value if:

Medical intervention is required to treat the patient, or

The abnormality leads to hospitalization.

- Inability to complete at least 75% of axitinib dosing or two infusions of MK-3475 within the 6-weeks DLT observation period due to treatment-related toxicity.

